### **5.3.7 Pharmacokinetic Variables**

Individual plasma concentrations of GLE and PIB will be measured for Part 1 and Part 2.

Values for the pharmacokinetic parameters of GLE and PIB including the  $C_{max}$ ,  $T_{max}$ ,  $C_{trough}$ , and area under the concentration curve (AUC) will be determined by non-compartmental methods using data from subjects who participate in the initial intensive PK sample collection and evaluation.

Individual model-predicted steady-state AUC values for GLE and PIB corresponding to the final proposed doses will be estimated by population pharmacokinetic analysis.

Additional parameters may be determined if useful in the interpretation of the data.

## **5.4 Removal of Subjects from Therapy or Assessment**

### **5.4.1 Discontinuation of Individual Subjects**

Each subject has the right to withdraw from the study at any time. In addition, the investigator may discontinue a subject from the study at any time if the investigator considers it necessary for any reason, including the occurrence of an adverse event or noncompliance with the protocol.

If a subject prematurely discontinues during the Treatment Period, Post-Treatment Period or the Long-term Follow-up Period, the procedures outlined for the applicable Premature D/C Visit should be completed as defined in [Appendix C](#). Ideally for study drug discontinuation, this should occur on the day of study drug discontinuation, but no later than 2 days after their final dose of study drug and prior to the initiation of any other anti-HCV therapy. However, these procedures should not interfere with the initiation of any new treatments or therapeutic modalities that the investigator feels are necessary to

treat the subject's condition. Following discontinuation of study drug, the subject will be treated in accordance with the investigator's best clinical judgment and monitored for HCV RNA and the emergence and persistence of resistant viral substitutions in the post-treatment period. The last dose of any study drug and reason for discontinuation from the Treatment Period will be recorded in the EDC system.

If a subject has an ongoing adverse event or an unresolved laboratory result that is significantly outside of the reference range at the time of study drug discontinuation, the investigator will attempt to provide follow-up until a satisfactory clinical resolution of the laboratory result or adverse event is achieved.

In the event that a positive result is obtained on a pregnancy test for a subject or a subject reports becoming pregnant during the Treatment Period, the DAAs may be continued at the investigator's discretion after discussion with the subject and parent(s)/guardian(s), if the benefit of continuing DAAs is felt to outweigh the potential risk. Specific instructions regarding subject pregnancy can be found in Section 6.1.6. Subjects will be monitored for SVR in the Post-Treatment Period as described in Section 5.1.3.

#### **5.4.1.1 HCV Virologic Failure Criteria**

The following criteria will be considered evidence of HCV virologic failure for the purposes of subject management:

- Confirmed increase from nadir in HCV RNA (defined as 2 consecutive HCV RNA measurements of  $> 1 \log_{10}$  IU/mL above nadir) at any time point during treatment; or
- Confirmed HCV RNA  $\geq 100$  IU/mL (defined as 2 consecutive HCV RNA measurements  $\geq 100$  IU/mL) after HCV RNA  $<$  LLOQ during treatment.

When confirmatory testing is required it should be completed as soon as possible and the subject should remain on study treatment until the HCV virologic failure criterion has been confirmed. Subjects meeting a virologic failure criterion will be discontinued from

study drug and will continue to be followed in the Post-Treatment Period for the emergence and persistence of resistant viral variants until 144 weeks post-treatment.

#### **5.4.1.2 Failure to Maintain HIV Virologic Suppression**

HIV-1 RNA will be assessed at scheduled study visits during the Treatment and Post-Treatment Period, as detailed in [Appendix C](#).

The criteria for failure to maintain HIV virologic suppression among subjects on stable ARTs is as follows:

- HIV-1 RNA  $\geq$  200 copies/mL confirmed on 2 consecutive tests at least 2 weeks apart, in a subject compliant with their HIV ART therapy.

At the time a confirmatory HIV-1 RNA is drawn, a sample for HIV-1 genotypic resistance testing should also be obtained; this sample may be analyzed if the subject's repeat plasma HIV-1 RNA is  $\geq$  500 copies/mL. A subject should remain on HCV study drug treatment and his/her current ART regimen while the failure to maintain HIV virologic suppression is being confirmed. A confirmatory HIV-1 RNA and HIV-1 genotypic resistance blood draw can be done as an unscheduled visit. However, if this blood draw falls on the date of

a scheduled study visit ([Appendix C](#)), only a single HIV-1 RNA and HIV-1 genotypic resistance blood draw needs to be performed at this visit.

During the Treatment Period, subjects with confirmed failure to maintain HIV-1 RNA suppression should continue study drug treatment unless there is a requirement for prohibited concomitant medications (see Section [5.2.3.1](#)) to construct a new HIV ART regimen.

Clinical management of failure to maintain HIV-1 virologic suppression during the study (Treatment Period and Post-Treatment Period) will be handled by the site investigator according to current HIV treatment guidelines and local standard of care.

If the investigator wishes to change the HIV-1 ART regimen for a subject, it must be discussed with the AbbVie Study Designated Physician prior to the change being made, unless the change is being made to address an immediate safety concern.

#### **5.4.2 Discontinuation of Entire Study**

AbbVie may terminate this study prematurely, either in its entirety or at any study site, for reasonable cause provided that written notice is submitted in advance of the intended termination. The investigator may also terminate the study at his/her site for reasonable cause, after providing written notice to AbbVie in advance of the intended termination. Advance notice is not required by either party if the study is stopped due to safety concerns. If AbbVie terminates the study for safety reasons, AbbVie will immediately notify the investigator by telephone and subsequently provide written instructions for study termination.

### **5.5 Treatments**

#### **5.5.1 Treatments Administered**

Each dose of open-label DAA study drugs (GLE and PIB) will be dispensed in the form of adult co-formulated tablets or a pediatric formulation. Study drugs will be dispensed at the visits listed in [Appendix C](#).

Part 1 Adult Formulations:

The study drug (GLE/PIB) will be dispensed in the form of co-formulated tablets at the visits listed in [Appendix C](#). Subjects will be instructed to take study drugs at the same time every day with food. Subjects will be instructed to swallow study drugs whole. Prior to all visits with pharmacokinetic sampling, the date and time of the two previous doses will be recorded to the nearest minute in the source documents and the eCRF.

GLE/PIB will be provided by AbbVie as 100 mg/40 mg film-coated tablets. GLE/PIB will be taken orally at GLE 300 mg/PIB 120 mg (three × GLE 100 mg/PIB 40 mg tablets) QD and with food.

Part 2 Pediatric Formulation:

Glecaprevir and Pibrentasvir (GLE/PIB) will be provided by the Sponsor as separate 15.67% and 8.25% film-coated pellets/granules. GLE/PIB will be taken orally and will be dosed QD based on body weight/age.

The film-coated pellets/granules are packed in unit doses and are to be administered at once QD into a dosing vehicle. The legal guardian(s) should be counselled by site to check that the study drug units have been emptied completely into the dosing vehicle to assure the complete dose is taken by the subject. A reference to the dosing vehicles is included in the dosing card to be used for Part 2.

For both Parts 1 and 2, on the morning of Study Day 1, at the site, subjects will be administered study drugs by the study site personnel and receive instructions for self-administration of all study drugs from the Day 1 through study Week 8, 12, or 16, depending on subject's genotype, treatment-experience and cirrhosis status, of the Treatment Period. The date and time of administration of the first dose of each drug will be recorded in the subject's source and eCRF.

Following enrollment, the site will use the IRT system for drug dispensation. Study drugs must not be dispensed without contacting the IRT system, and only for subjects enrolled in the study through the IRT system.

All subjects who receive at least one dose of study drugs who fail to achieve virologic suppression, or who experience virologic breakthrough on DAA therapy will be discontinued from treatment and enter the Post-Treatment Period, unless alternative management is agreed to with Primary Therapeutic Area Medical Director. The investigator can prescribe another regimen, as deemed appropriate, which will not be provided or reimbursed by AbbVie.

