**Table 6. Treatment Regimen and Duration (Subjects in Japan)**

Patient Population	Duration
GT1 – 2 NC, TN, TE – IFN	8 weeks
GT1 – 2 C, TN, TE – IFN GT3 – 6 NC, C, TN, TE – IFN GT1 – 6 TE – SOF	12 weeks

Legend: C = Cirrhotic; NC = Non-Cirrhotic; TE – IFN = Japan Treatment experienced to IFN (alpha, beta or pegIFN) ± RBV; TE – SOF = Japan Treatment experienced to SOF/RBV; TN = Treatment Naïve

GLE/PIB will be administered as described in Section 5.5.1 (Treatments Administered). Subjects and their parent(s)/guardian(s) will receive instructions about the study drugs at the Day 1 Visit. The study drugs will be dispensed at the visits as indicated in [Appendix C](#).

After the Day 1 visit, all subjects will continue to return to the site on an outpatient basis for the study visits and procedures as identified in [Appendix C](#). Subjects could also return to the site for an unscheduled study visit for additional safety assessments if the investigator or sponsor feels it is necessary. Sites should ensure that subjects adhere to the study visits listed in [Appendix C](#). Subjects who cannot complete their study visit per the visit schedule should ensure they do not run out of study drug prior to their next study

visit. Study drug compliance is critical to ensure adequate drug exposure and optimal treatment outcome.

Virologic failure criteria will be evaluated and applied by the Investigator as detailed in Section 5.4.1.1.

Subjects who prematurely discontinue from the Treatment Period should return for a Treatment Discontinuation Visit and undergo the study procedures as outlined in [Appendix C](#) and as described in Section 5.5.1. Ideally, this should occur on the day of study drug discontinuation, but is recommended to be no later than 2 days after their final dose of study drug and prior to the initiation of any other anti-HCV therapy if applicable. Following completion or premature discontinuation of study drug treatment, all subjects in either Part 1 or Part 2 will be followed in the associated Post-Treatment Period of Part 1 or Part 2.

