5.1.2 Modified Intention-to-Treat (mITT) Population

Sensitivity analyses of SVR₁₂ as described in Section 10.5 will be performed on the ITT population modified to exclude subjects who did not achieve SVR₁₂ for reasons other than virologic failure (mITT-VF).

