10.0 Efficacy Analysis

10.1 General Considerations

General Considerations

All efficacy analyses will be performed on the ITT population, unless otherwise specified.

Missing data will be imputed as described in Section 6.3 for analyses of the HCV RNA endpoints of SVR.

Plasma HCV RNA levels will be determined for each sample collected by the central laboratory using the Roche COBAS® AmpliPrep/COBAS® TaqMan® HCV Quantitative Test, v2.0. The lower limit of detection (LLOD) and lower limit of quantification (LLOQ) for this assay (regardless of genotype) are both 15 IU/mL.

HCV RNA results that are detectable but not quantifiable are reported as "< 15 IU/ML HCV RNA DETECTED" and those that are undetectable are reported as "HCV RNA NOT DETECTED" in the database.

The notation "HCV RNA < LLOQ" is used to represent all HCV RNA values < 15 IU/mL, including values reported as "HCV RNA NOT DETECTED" or "< 15 IU/ML HCV RNA DETECTED." HCV RNA \geq LLOQ are all quantifiable values of 15 IU/mL or greater.

Definitions for Efficacy Endpoints

A confirmed quantifiable value during treatment is defined as any two consecutive HCV RNA measurements \geq LLOQ (or 100 IU/mL for **Breakthrough**), either both during treatment or at the final treatment measurement and the next consecutive post-treatment measurement. A confirmed quantifiable post-treatment value is defined as any two consecutive post-treatment HCV RNA measurements \geq LLOQ.

Breakthrough = confirmed HCV RNA \geq 100 IU/mL after HCV RNA < LLOQ during the Treatment Period; or confirmed increase from nadir in HCV RNA (two consecutive HCV RNA measurements $> 1 \log_{10}$ IU/mL above nadir) at any time point during the Treatment Period. A single breakthrough value (\geq 100 IU/mL or $> 1 \log_{10}$ above nadir) followed by lost to follow-up also will be considered a breakthrough (i.e., will not require confirmation).

EOT failure = HCV RNA \geq LLOQ at end of treatment with at least 6 weeks of treatment, where the HCV RNA value must be collected on or after Study Drug Day 36 and study drug duration \geq 36 days.

On-treatment virologic failure = **Breakthrough** or **EOT failure**; if a subject meets both definitions of Breakthrough and EOT failure, he or she will be categorized as Breakthrough only.

SVR₄ = HCV RNA $<$ LLOQ in the SVR₄ window (4 weeks after the last actual dose of study drug) without any confirmed quantifiable (\geq LLOQ) post-treatment value before or during that SVR window.

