HCV reinfection is defined as confirmed HCV RNA \geq LLOQ after the end of active treatment in a subject who had HCV RNA $<$ LLOQ at Final Treatment Visit, along with the post-treatment detection of a different HCV genotype, subtype, or clade compared with baseline, as determined by phylogenetic analysis of the NS3 or NS5A, and/or NS5B gene sequences. Reinfection in the case of the same HCV subtype is defined as a clade switch, as indicated by the lack of clustering between the baseline and post-treatment sequences by phylogenetic analysis. If phylogenetic analysis is not possible due to technical difficulties, HCV reinfection may be determined with a confirmed HCV genotype or subgenotype switch by the Versant HCV Genotype Inno-LiPA Assay v2.0 or Sanger assay.

Post-treatment relapse is defined as described earlier (**Relapse₁₂**, **Relapse₂₄**, **Relapse_{overall}**), and no genotype, subtype, or clade switch compared with baseline as determined by phylogenetic analysis of the NS3 or NS5A gene sequences. If phylogenetic analysis is not possible due to technical difficulties, the subject will be defined as having a post-treatment relapse unless an HCV genotype or subtype switch is confirmed by the Versant HCV Genotype Inno-LiPA Assay v2.0 or Sanger assay.

Reasons for SVR₁₂ Non-Response

Subjects who do not achieve SVR₁₂ (SVR₁₂ non-responders) will be categorized as having:

1. On-treatment virologic failure (see **On-treatment virologic failure** definition);

2. HCV reinfection (see definition described earlier);
3. Relapse₁₂;
4. Prematurely discontinued study drug with no on-treatment virologic failure (defined as any SVR₁₂ non-responder who prematurely discontinued study drug [study drug duration < 52 days for subjects assigned to 8 weeks of treatment, < 77 days for subjects assigned to 12 weeks of treatment, and < 103 days for subjects assigned to 16 weeks of treatment] and did not meet the **On-treatment virologic failure or reinfection** definitions);
5. Missing follow-up data in the SVR₁₂ window (defined as any subject who completed study drug without data in the SVR₁₂ window after applying the imputation rules and not meeting the definitions of [1], [2], [3], or [4]);
6. Other (defined as any SVR₁₂ non-responder not meeting the definitions of [1] – [5]).

Reasons for SVR₂₄ Non-Response

Subjects who do not achieve SVR₂₄ (SVR₂₄ non-responders) will be categorized as having:

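### Protocol 5.5.1 and 5.4.1.1 set different virologic stopping rules, and SAP 10.1 counts an SVR12 non-responder stopped for non-suppression before Day 36, without rebound, as a non-virologic dropout

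*Protocol*

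**What the plan says.** **Stopping rules.** Protocol 5.5.1 states that subjects "who fail to achieve virologic suppression, or who experience virologic breakthrough on DAA therapy will be discontinued from treatment and enter the Post-Treatment Period". The same sentence makes this stop waivable by agreement with the sponsor's medical director. It does not say when, at what HCV RNA level or after how many measurements a subject has failed to suppress.

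Protocol 5.4.1.1 opens with "The following criteria will be considered evidence of HCV virologic failure for the purposes of subject management" and gives two criteria. The first begins "Confirmed increase from nadir in HCV RNA" and needs two consecutive values more than 1 log10 above nadir. The second needs two consecutive values of at least 100 IU/mL after a value below LLOQ. Both describe rebound during treatment. A subject meeting either is to be discontinued, and no exception is written there. Protocol 5.1.2 points to this section: "Virologic failure criteria will be evaluated and applied by the Investigator as detailed in Section 5.4.1.1".

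**Classification.** SAP 10.1 recognises on-treatment virologic failure in two forms. Breakthrough uses the same two rebound patterns. EOT failure means that HCV RNA is still quantifiable when treatment stops. It applies only "with at least 6 weeks of treatment, where the HCV RNA value must be collected on or after Study Drug Day 36". In addition, the duration on drug has to be 36 days or more. Protocol 8.1.2.2 likewise sets a six-week minimum. The fourth reason for SVR12 non-response in SAP 10.1 is "Prematurely discontinued study drug with no on-treatment virologic failure". SAP 5.1.2 removes from mITT-VF every SVR12 non-responder whose reason is not virologic failure.

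**The concern.** The two sections can give different instructions for one child. A child whose HCV RNA is falling but still quantifiable at Week 4 meets no criterion in 5.4.1.1 and stays on drug, while 5.5.1 can be read as requiring a stop. Even for breakthrough, which both sections cover, stopping is mandatory in 5.4.1.1 and waivable in 5.5.1.

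The SAP has no place for the extra trigger in 5.5.1 when it acts early. A child taken off drug because the virus was not suppressed could be reported as having had no on-treatment virologic failure. That affects a secondary endpoint, the reasons for non-response, the mITT-VF sensitivity analysis and the grouping of resistance data, always in the drug's favour.

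**Working it through.** The documents state no figure for this point, so the check is a trace through the definitions followed by a one-child illustration.

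**Trace.** Assume a child who never falls below LLOQ on treatment, whose last on-treatment value is not more than 1 log10 above nadir, who is stopped before Day 36 and who does not reach SVR12.

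1. *Breakthrough (SAP 10.1)?* No. The 100 IU/mL arm needs an earlier value below LLOQ, and the nadir arm needs a rise of more than 1 log10.
2. *EOT failure?* No. The value and the drug duration must both reach Day 36.
3. *Reinfection or relapse?* No. Both require HCV RNA below LLOQ at the Final Treatment Visit. Relapse also requires completed treatment, meaning at least 52, 77 or 103 days for 8, 12 or 16 weeks.
4. *Reason for non-response?* Category 4, premature discontinuation without on-treatment virologic failure.
5. *Consequences?* The child is outside the SAP's definition of virologic failure, so is excluded from mITT-VF and placed in the non-PVF resistance group (SAP 10.8.1). An adolescent would also drop out of resistance Analyses 2 and 3, which use mITT-VF in Cohort 1.

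Result by stop day, the same for all three assigned durations:

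- Day 14, 28 or 35: category 4.
- Day 36, 42 or 56, with HCV RNA still at or above LLOQ: EOT failure.

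Two scheduled on-treatment HCV RNA visits, Week 2 (Day 14) and Week 4 (Day 28), fall before the switch at Day 36.

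**SVR12 non-response is plausible on this path.** Protocol 5.5.1 lets the investigator prescribe another regimen. SAP 6.3 counts a child who starts new HCV treatment as a failure at all later time points.

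**Size.** Inputs: N = 125 (Protocol 8.2; 44 + 81 = 125 in Protocol 5.1) and about 22 per Part 2 age group on the final dose (Protocol 5.5.3). Assumption: exactly one such child and no other non-responder. The 95% intervals are Wilson, as the SAP uses for these two analyses, with z = 1.96:

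centre = (p + z²/2n)/(1 + z²/n); half-width = z·√[p(1−p)/n + z²/4n²]/(1 + z²/n)

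| | As SAP classifies | If counted as virologic failure |
|---|---|---|
| On-treatment failure, N = 125 | 0/125 = 0.0% (0.0 to 3.0) | 1/125 = 0.8% (0.1 to 4.4) |
| mITT-VF SVR12, N = 125 | 124/124 = 100% (97.0 to 100) | 124/125 = 99.2% (95.6 to 99.9) |
| On-treatment failure, N = 22 | 0/22 = 0.0% (0.0 to 14.9) | 1/22 = 4.5% (0.8 to 21.8) |
| mITT-VF SVR12, N = 22 | 21/21 = 100% (84.5 to 100) | 21/22 = 95.5% (78.2 to 99.2) |

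ITT SVR12 is 124/125 or 21/22 under both classifications.

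**The case against.** **5.4.1.1 is the operative rule.** Protocol 5.1.2 names it, and 5.5.1 is a dispensing section whose wording echoes the endpoint phrase for failure to suppress at the end of treatment. The early stop is therefore permitted by the text, not scheduled by it. That limit stands. The echo does not remove the conflict, however: at the planned end of treatment an instruction to discontinue would do nothing, so the words have effect only during treatment.

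**Investigators can stop anyone anyway.** Protocol 5.4.1 allows discontinuation at any time for any reason, so uneven treatment lengths do not arise from this mismatch alone. That stands, but it does not answer the classification problem.

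**The child stays visible.** The SAP lists non-responders by reason and subjects excluded from mITT-VF, and it summarises discontinuation reasons. A reader could find one child among 125. The tabulated rates would still carry the wrong label.

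**The minimum duration is agreed.** It appears in both Protocol 8.1.2.2 and SAP 10.1. This is a good reason to keep it for early stops unrelated to response.

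A reader might also infer three stronger points that the documents do not support:

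- *SVR12 itself is biased.* One child is 1/125 = 0.8 points, but ITT SVR12 does not depend on the classification. Whether a shortened course costs a response cannot be derived from the documents.
- *Resistance data would be lost.* Protocol 8.1.6.1 and SAP 10.8.1 call for sequencing non-responders without virologic failure who have HCV RNA of at least 1000 IU/mL after stopping. Only the reporting group changes.
- *Day 36 contradicts six weeks (42 days).* The SAP clause gives six weeks an operational limit. Its 6-day allowance resembles those for completed treatment: 56 − 52 = 4, 84 − 77 = 7 and 112 − 103 = 9 days. The lower limit also captures more failures, not fewer.

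**Conclusion.** The concern holds in two linked parts. First, Protocol 5.5.1 and 5.4.1.1 differ in trigger and in exception and must be reconciled; this follows from the text alone. Second, if 5.5.1 is applied to stop a child for non-suppression before Day 36, and that child has not rebounded and misses SVR12, the SAP reports the child as a non-virologic dropout.

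The effect is one subject per case in on-treatment virologic failure, the reasons for non-response, mITT-VF and the PVF/non-PVF split. The frequency is not given and is probably small: the Protocol introduction reports 23 virologic failures of any kind among the adult treatment-naïve and TE-PRS subjects, against 2,256 in its Table 3 (23/2,256 = 1.0%). The one-child figures are an illustration, not a forecast. No hypothesis test is affected, since SAP 10.2 plans none for the efficacy endpoints. The point deserves correction because the error runs in one direction and is cheap to remove.

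**What to change.** 1. **Protocol.** The sponsor should reconcile 5.5.1 and 5.4.1.1 into one set of virologic stopping triggers with one exception clause, cited from both places and from 5.1.2. No view is taken here on which triggers or exception are right.
2. **SAP 10.1.** Classify as on-treatment virologic failure any subject whose recorded reason for stopping is lack of virologic response and whose last on-treatment HCV RNA is at or above LLOQ, and keep that subject in mITT-VF. Leave the minimum-duration rule as it is for all other early stops. Because Protocol 8.1.2.2 carries the same minimum, align it or record the difference in SAP 12.1.

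The cost is one protocol wording change and one SAP definition. Protocol 5.4.1 already has the reason for discontinuation recorded. The eCRF reason codes are not shown, so this assumes that they can identify lack of virologic response. The downside is that on-treatment failure may rise, and mITT-VF SVR12 fall, by a subject or so.
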